#### **11.1.4 Pharmacokinetic Analysis Set**

The Pharmacokinetic Analysis Set is defined as patients who received at least 1 dose of the study drug, who provided specimens for pharmacokinetic assessment, and who have available measurement data obtained with the specimens.

#### **11.1.5 Pharmacodynamic (Biomarker) Analysis Set**

The Pharmacodynamic (Biomarker) Analysis Set is defined as patients who received at least 1 dose of the study drug, who provided specimens for the biomarker study, and who have available data on FLT3-ITD status obtained with the specimens.

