### 6.8.1 FLT3-ITD Status and c-KIT Mutations

The following specimens will be collected before the start of administration of coadministered drugs (cytarabine and the anthracycline drug): 1 mL of bone marrow liquid or 2 mL of peripheral blood for analysis of the FLT3-ITD status, and 1 mL of bone marrow liquid or 7 mL of peripheral blood for analysis of c-KIT mutations. The specimens under refrigeration will be submitted to the agency contracted by the sponsor to collect the specimens.

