### 6.8.2 Phosphorylated FLT3, STAT5, and c-KIT Protein Levels in Blood

After 2 mL of blood is collected from each patient as specified in "Table 6.8-1 Blood Collection Points (Phosphorylated Protein Levels in Blood)," the plasma specimens will immediately be stored in a frozen state at  $-90^{\circ}\text{C}$  to  $-70^{\circ}\text{C}$ . The specimens in a frozen state will be submitted to the agency contracted by the sponsor to collect the specimens.

Table 6.8-1 Blood Collection Points (Phosphorylated Protein Levels in Blood)

Treatment Cycle	Treatment Day	Blood Collection Point (Acceptable Limit)
Remission induction therapy	Day 8	Pre-dose
Cycle 1	* First day of quizartinib administration	2 hours ( $\pm 10$ minutes) post-dose
		4 hours ( $\pm 10$ minutes) post-dose
		6 hours ( $\pm 10$ minutes) post-dose
	Day 9	Pre-dose
	Day 15	Pre-dose
	Day 21	Pre-dose
	* Last day of quizartinib administration	

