### 6.8.3 Inhibitory Activity of Plasma Quizartinib on Phosphorylated FLT3 Protein

After 5 mL of blood is collected from each patient as specified in “Table 6.8-2 Blood Collection Points (Inhibitory Activity of Plasma Quizartinib on Phosphorylated FLT3 Protein),” the specimens will be prepared and immediately be stored in a frozen state at  $-90^{\circ}\text{C}$  to  $-70^{\circ}\text{C}$ . The specimens in a frozen state will be submitted to the agency contracted by the sponsor to collect the specimens.

Table 6.8-2 Blood Collection Points (Inhibitory Activity of Plasma Quizartinib on Phosphorylated FLT3 Protein)

Treatment Cycle	Treatment Day	Blood Collection Point (Acceptable Limit)
Remission induction therapy	Day 8	Pre-dose
Cycle 1	* First day of quizartinib administration	2 hours ( $\pm 10$ minutes) post-dose
		4 hours ( $\pm 10$ minutes) post-dose
		6 hours ( $\pm 10$ minutes) post-dose
	Day 9	Pre-dose
	Day 15	Pre-dose
	Day 21	Pre-dose
	* Last day of quizartinib administration	

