#### **11.3.5 Pharmacodynamic (Biomarker) Analysis**

In the Pharmacodynamic (Biomarker) Analysis Set, frequency tables will be prepared for

the FLT3-ITD status and the c-KIT mutation status. For phosphorylated FLT3, STAT5, and c-KIT protein levels in blood and the inhibitory activity of plasma quizartinib on phosphorylated FLT3 protein, the measured values will be summarized at each time point.

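### The biomarker analysis set requires an FLT3-ITD result, so one failed FLT3-ITD sample takes a treated patient out of the c-KIT, phosphoprotein and plasma-inhibition tables as well

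*Combined protocol and SAP*

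**What the plan says.** Section 11.1.5 sets three conditions for the Pharmacodynamic (Biomarker) Analysis Set: at least one dose of study drug, biomarker specimens provided, and membership limited to patients "who have available data on FLT3-ITD status obtained with the specimens".

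Section 11.3.5 opens with the population: "In the Pharmacodynamic (Biomarker) Analysis Set, frequency tables will be prepared for" FLT3-ITD status and c-KIT mutation status. It then turns to the repeated measures: "For phosphorylated FLT3, STAT5, and c-KIT protein levels in blood and the inhibitory activity of plasma quizartinib" on phosphorylated FLT3, where "the measured values will be summarized at each time point". That second sentence names no population of its own, and no other set is offered for these endpoints anywhere in section 11.

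The specimens are described separately:

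- FLT3-ITD (section 6.8.1), before chemotherapy: "1 mL of bone marrow liquid or 2 mL of peripheral blood for analysis of the FLT3-ITD status".
- c-KIT mutation (section 6.8.1), a further amount at the same stage: "1 mL of bone marrow liquid or 7 mL of peripheral blood for analysis of c-KIT mutations".
- Phosphoproteins (section 6.8.2): "After 2 mL of blood is collected from each patient as specified in" Table 6.8-1.
- Plasma inhibitory activity (section 6.8.3): "After 5 mL of blood is collected from each patient as specified in" Table 6.8-2.

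**The concern.** The entry condition belongs to one assay but controls the tables for four groups of endpoints. FLT3-ITD is determined once, before cytarabine and the anthracycline start. The phosphoprotein and inhibition samples are drawn on Days 8, 9, 15 and 21 of induction Cycle 1. Either can fail while the other succeeds. FLT3-ITD status is not an eligibility criterion (section 4.1.1), so a patient without a result can still be enrolled, dosed and sampled.

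The outlined summaries do not use FLT3-ITD status as a stratifier, so they can be produced without it. The neighbouring Pharmacokinetic Analysis Set (section 11.1.4) asks only for measurements from its own specimens, and no reason is given for treating biomarkers differently. At stake is the completeness of small descriptive tables for a secondary objective.

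**Working it through.** **Planned N.** Section 11.5 plans 6 to 12 patients. The 3 + 3 scheme at two levels reproduces this: 2 × 3 = 6 and 2 × 6 = 12.

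**Share of patients lost per failed FLT3-ITD result.**

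- Whole study: 1/6 = 17% down to 1/12 = 8%.
- Within a level: 1/3 = 33% with three patients, 1/6 = 17% with six.

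**Data excluded per patient.** Tables 6.8-1 and 6.8-2 list the same time points: Day 8 at pre-dose, 2, 4 and 6 hours, then Days 9, 15 and 21 at pre-dose, so 4 + 1 + 1 + 1 = 7.

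- Samples: 7 phosphoprotein + 7 inhibition = 14.
- Samples after the first quizartinib dose: the Day 8 pre-dose sample precedes it, so 6 + 6 = 12.
- Values: three phosphoproteins × 7 = 21, plus 7 inhibition values = 28.
- With the single c-KIT mutation result: 28 + 1 = 29.

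**How likely is at least one such loss?** The documents give no FLT3-ITD failure rate. With an assumed rate f, independent between patients, the chance of at least one failure among n patients is 1 − (1 − f)^n. For example, with f = 5% and n = 6: 1 − 0.95^6 = 26.5%.

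| Assumed f | n = 3 | n = 6 | n = 12 |
|---|---|---|---|
| 2% | 5.9% | 11.4% | 21.5% |
| 5% | 14.3% | 26.5% | 46.0% |
| 10% | 27.1% | 46.9% | 71.8% |
| 20% | 48.8% | 73.8% | 93.1% |

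These figures show a range; they do not predict the rate in this trial.

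**With an endpoint-specific rule.** The same patient would be absent only from the FLT3-ITD frequency table. The other tables would keep 3 of 3 (or 6 of 6) patients at that level instead of 2 of 3 (or 5 of 6).

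**The case against.** **FLT3-ITD status matters for reading these assays.** Section 1.3.1 reports that wild-type FLT3 needed higher doses and longer exposure than FLT3-ITD before phosphorylated FLT3 became undetectable. It also reports a stronger pSTAT5 effect in FLT3-ITD positive patients. Section 6.8 includes a search for predictive biomarkers. Known status for everyone also gives one common denominator. A reader might infer that the condition serves no purpose, and these passages do not support that. Equally, they do not make it necessary. The same section reports pSTAT5 decreases in 10 of 11 FLT3-ITD positive and 7 of 9 negative patients, and concludes that inhibition occurs in both groups. This favours an added breakdown by status, not removal from pooled tables.

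**The data are not lost.** A reader might infer that the values are thrown away. The rule restricts set-based tables; nothing deletes values or bars them from listings. This stands as a limit on the point.

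**The sponsor has discretion.** Section 11.1 lets the sponsor settle flags, but only for patients not already covered by the protocol or SAP, and this patient is covered, as outside the set. Section 11.2 concerns the handling of individual data. Section 11.4 permits documented changes to planned analyses. None clearly restores the patient, and flags are finalized after CRF lock in an open-label study, so a rule fixed beforehand is cleaner.

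**The SAP may resolve it.** Section 11 calls itself an outline and defers details to the SAP. The supplied document has no SAP text on biomarker populations, so endpoint-specific denominators or summaries by FLT3-ITD status may exist there. This stands.

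**The trigger may be rare.** FLT3-ITD can be run on marrow or blood, and a marrow assessment is required before registration, so there is more than one possible specimen source. Patients who decline the biomarker study (section 15.4) would lack these data under either definition. The change helps only with isolated FLT3-ITD failures.

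**Conclusion.** The point holds as a minor defect in a set definition. Read together, sections 11.1.5 and 11.3.5 exclude a treated patient without an FLT3-ITD result from every biomarker table, including those built from separate specimens and not split by that status. This reading takes the set named at the start of section 11.3.5 to govern the whole section, which is the natural reading because no other set is named.

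The amounts in the working are the maximum per patient, assuming all scheduled samples are taken and yield results. A reader might count all 14 samples as post-baseline. The documents do not support that, because each assay's first sample precedes quizartinib.

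Nothing here touches the DLT, MTD, safety or pharmacokinetic conclusions, which use other sets. The biomarker objective is secondary and exploratory (section 2), and the summaries are descriptive.

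**What to change.** In section 11.1.5, replace the FLT3-ITD condition so that the set comprises patients with at least one dose of study drug and available data on at least one biomarker. In section 11.3.5, add that each endpoint is summarised in the patients with data for it, with N shown in each table. Require FLT3-ITD status only for tables of FLT3-ITD or by FLT3-ITD status, with an unknown category if needed. Align the SAP with this wording.

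The change costs a phrase and a sentence, and no extra samples or visits. It has a small downside: denominators may differ between endpoints, and pooled summaries may include patients of unknown FLT3-ITD status. Showing N per table and flagging unknown status in the listings makes both visible.

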### **11.2 Data Handling**

The sponsor will decide the handling of individual data in consultation with the medical expert and lock data.

### **11.3 Statistical Analysis Items and Methods**

#### **11.3.1 Baseline Subject Characteristics**

To analyze baseline subject characteristics (demographic variables and other baseline characteristics), frequency tables will be prepared for categorical data and summary statistics will be calculated for quantitative data. Analyses will be performed on the Safety Analysis Set, Efficacy Analysis Set, MTD Analysis Set, Pharmacokinetic Analysis Set, and Pharmacodynamic (Biomarker) Analysis Set.

#### **11.3.2 Safety Analysis**

Other safety analyses than DLT analyses will be performed on the Safety Analysis Set, whereas DLT analyses will be performed on the MTD Analysis Set.

AEs that occur or worsen relative to the pre-treatment state after the start of study treatment (treatment emergent AEs [TEAEs]) will be tabulated. AEs collected in the study will be coded using the Medical Dictionary for Regulatory Activities (MedDRA) terminology developed by the International Conference on Harmonisation of Technical Requirements for Registration of Pharmaceuticals for Human Use (ICH), and be

tabulated by body organ group using the MedDRA system organ class (SOC) and by AE term using preferred terms (PT).

#### **11.3.2.1 Adverse Events**

For all TEAEs and TEAEs assessed as “related” to the study drug or a coadministered drug (cytarabine or the anthracycline drug), frequency tables will be prepared for patients with TEAEs as classified below.

The grade of each AE will be assessed according to the CTCAE v4.0 Japanese version.

- TEAEs (by grade; including classification into  $\geq$  Grade 3 events and others)
- Serious TEAEs
- Patients who have postponed administration of the study drug due to TEAEs
- Patients who have postponed administration of a coadministered drug (cytarabine or the anthracycline drug) due to TEAEs
- Patients with treatment discontinuation because of TEAE

#### **11.3.2.2 Individual Adverse Events**

For all TEAEs and TEAEs assessed as “related” to the study drug or a coadministered drug (cytarabine or the anthracycline drug), frequency tables will be prepared according to the following categories. If a patient reports the same event several times, only the highest-grade event will be counted for tabulation by grade.

- TEAEs
- TEAEs by grade (including classification into  $\leq$  Grade 2 events and  $\geq$  Grade 3 events)
- TEAEs leading to postponement of administration of the study drug
- TEAEs leading to postponement of administration of a coadministered drug (cytarabine or the anthracycline drug)
- TEAEs causing treatment discontinuation

#### **11.3.2.3 Dose-limiting Toxicity**

DLTs will be summarized by frequency tables.

#### **11.3.2.4 Laboratory Data**

For hematology and blood chemistry tests, summary statistics of measured values and changes from baseline will be calculated at each time point. For urinalysis (except specific gravity), shift tables of measured values at baseline and those at each time point

will be prepared. For specific gravity, summary statistics will be calculated at each time point.

#### **11.3.2.5 Vital Signs and Body Weight**

For blood pressure (systolic and diastolic), pulse rate, body temperature, and body weight, summary statistics of measured values and changes from baseline will be calculated at each time point.

#### **11.3.2.6 12-lead Electrocardiogram**

For 12-lead ECG findings, shift tables of normal-abnormal assessments before the first dose of the study drug and at each time point will be prepared. For PR, QRS, RR, QT, and QTcF intervals and heart rate, summary statistics of measured values and changes from baseline will be calculated at each time point. For QTcF, frequency tables will be prepared according to the following categories.

Increase in absolute QTcF:

- QTcF > 450 ms
- QTcF > 480 ms
- QTcF > 500 ms

Changes in QTcF from baseline:

- Increase in QTcF from baseline > 30 ms
- Increase in QTcF from baseline > 60 ms

#### **11.3.3 Efficacy Analysis**

In the Efficacy Analysis Set, frequency tables will be prepared for CR, CRp, CRi, PR, and NR at each time point as well as for best response. The CRc rate (CR + CRp + CRi), response rate (CRc + PR), and their 95% confidence intervals will be calculated.

#### **11.3.4 Pharmacokinetic Analysis**

In the Pharmacokinetic Analysis Set, summary statistics of the plasma concentrations of quizartinib and AC886 will be calculated by dose at each time point, and plasma concentration-time profiles will be prepared. Summary statistics of pharmacokinetic parameters will also be calculated.

#### **11.3.5 Pharmacodynamic (Biomarker) Analysis**

In the Pharmacodynamic (Biomarker) Analysis Set, frequency tables will be prepared for

the FLT3-ITD status and the c-KIT mutation status. For phosphorylated FLT3, STAT5, and c-KIT protein levels in blood and the inhibitory activity of plasma quizartinib on phosphorylated FLT3 protein, the measured values will be summarized at each time point.

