### **1.3 Clinical Study Data**

#### **1.3.1 Phase 1 Study (Study CP0001)**

Quizartinib was tested in 76 AML patients with treatment cycles of intermittent dosing (14 days on the drug followed by 14 days of rest) at doses of 12 mg/day to 450 mg/day, and 28-day continuous dosing at 200 and 300 mg/day.

Dose-limiting toxicities (DLTs) were pyrexia in 1 of 5 patients on intermittent dosing at 135 mg/day, Grade 3 QTc prolongation in 1 of 17 patients on continuous dosing at 200 mg/day, and Grade 3 QTc prolongation in 3 of 8 patients on continuous dosing at 300 mg/day. The maximum tolerated dose (MTD) was determined to be 200 mg/day continuous dosing.

The overall response rate (CR + partial remission [PR]) was 53% in FLT3-ITD positive patients and 14% in FLT3-ITD negative patients.

In this study, plasma specimens were collected from quizartinib-treated patients and were tested in an ex vivo assay of plasma inhibitory activity of quizartinib on FLT3 phosphorylation. Plasma from the patients suppressed FLT3-ITD and wild-type FLT3 (FLT3-WT) autophosphorylation activity. In cells expressing FLT3-WT, higher doses and longer exposures of quizartinib were necessary to eliminate detectable phosphorylated FLT3 as compared with FLT3-ITD-expressing cells.

Moreover, a subset of 20 AML patients in the study were evaluated for the effect of quizartinib on phosphorylated STAT5 (pSTAT5), using a whole blood-based assay. Quizartinib treatment decreased pSTAT5 levels in 10 of 11 FLT3-ITD positive patients and 7 of 9 FLT3-ITD negative patients. There was an enhanced effect on pSTAT5 inhibition in FLT3-ITD positive patients. These data suggest that quizartinib inhibits pSTAT5 production regardless of FLT3-ITD mutation status in AML patients.

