#### **15.4 Informed Consent for Pharmacogenomics/Biomarker Study**

The investigator or subinvestigator will explain the details of the study listed below to subject candidates in a readily understandable way to confirm their willingness to provide consent to participate in the biomarker study by their free will, and obtain the result in writing. The informed consent forms for the core clinical study and the biomarker study will be prepared in a one-unit format. The investigator or subinvestigator will ensure that the subject's decision on the consent has been entered in the concerned section of the informed consent form.

- 1) Characteristics and properties of genetic information
- 2) Study objectives
- 3) Study methods
- 4) Foreseeable physical and mental benefits and risks associated with the study
- 5) Statements that participation in the pharmacogenomics study is based on the subject's own free will and that the subject can refuse to participate in, or withdraw from, the study at any time; that he/she will not be disadvantaged even if he/she withdraws his/her consent; that participation in the core study will not be affected by

refusal to participate in the biomarker study.

- 6) Handling of specimens and data after withdrawal of consent
- 7) Matters on the method of handling, duration of storage, and disposal of specimens
- 8) Compensation and treatment that the subject can receive
- 9) Disclosure of study results and to whom the results belong
- 10) Details of expenses the subject needs to pay, if any
- 11) A statement that no payment is made for specimens provided by the subject
- 12) Protection of human rights, including the subject's privacy

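### The phosphoprotein biomarkers are summarised only as raw values per time point, so within-patient change from the scheduled Day 8 pre-dose sample goes unreported and a quizartinib effect may be obscured

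*Combined protocol and SAP*

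**What the plan says.** Section 11.3.5 covers pFLT3, pSTAT5, phosphorylated c-KIT and the plasma assay in one sentence, which ends "inhibitory activity of plasma quizartinib on phosphorylated FLT3 protein, the measured values will be summarized at each time point". The synopsis says the same. Neither mentions change, ratio, percent of pre-dose or a count of patients with a decrease. Section 11.3.5 does not say that the summaries are by dose.

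Other parts of the plan differ:

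- For hematology and chemistry (Section 11.3.2.4), "summary statistics of measured values and changes from baseline will be calculated at each time point". Sections 11.3.2.5 and 11.3.2.6 plan the same for vital signs, body weight and ECG intervals.
- Plasma concentration summaries "will be calculated by dose at each time point" (Section 11.3.4).
- Section 6.8.2 begins "After 2 mL of blood is collected from each patient as specified in" Table 6.8-1. That table lists Day 8 pre-dose and 2, 4 and 6 hours post-dose, then pre-dose on Days 9, 15 and 21. Section 6.8.3 sets the same schedule for the plasma assay.
- Biomarker consent is separate. Under Section 15.4, "participation in the core study will not be affected by" refusing it.

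**The concern.** Whether quizartinib lowers a phosphoprotein is a question about change within a patient. The sampling is paired, but the planned summary is not. The introduction reports the earlier Phase 1 study in within-patient terms: "Quizartinib treatment decreased pSTAT5 levels in 10 of 11 FLT3-ITD positive patients and 7 of 9 FLT3-ITD negative patients" (Section 1.3.1). Tables of raw values per visit cannot give a count of that kind. Section 6.8 also hopes to find biomarkers that predict efficacy, which needs one response value per patient.

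The groups are very small. At 3 patients, one missing sample removes a third of the data at that visit; at 6 patients, a sixth. Samples may well be missing, because quizartinib is interrupted while certain concomitant drugs are used (Sections 5.5 and 5.7) and patients may be withdrawn (Section 5.6). A raw mean can then move because the patients contributing to it have changed. At stake is how well the exploratory biomarker objective can be read, not any dose decision.

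**Working it through.** **The plan's own figure.** Section 11.5 gives 6 to 12 patients. Two levels of 3 make 6; two levels of 3 + 3 make 12. The range is reproduced, with 3 to 6 patients per level. The plan states no SD, effect size or power for the biomarkers, so there is nothing further to reproduce.

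**What raw summaries retain.** With complete data, the mean change equals the difference between the visit means (on the log scale, the ratio of geometric means), so it can be read from the planned tables. Its spread cannot, because that needs the within-patient correlation rho: SD(change) = SD(raw) × √(2(1 − rho)). The number of patients with a decrease cannot be read from these tables either.

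**What pairing could gain.** Assumptions (none is in the documents): a log-normal marker, a between-patient CV of 50% or 100%, and rho of 0.5, 0.7 or 0.9. The log SD is s = √ln(1 + CV²), which is 0.472 at 50% and 0.833 at 100%. The 95% interval for the post/pre ratio is the estimate multiplied and divided by:

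- unpaired (all that raw tables allow): exp[t(2n − 2) × s × √(2/n)]
- paired: exp[t(n − 1) × s × √(2(1 − rho)/n)]

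Example with n = 6, CV 50%, rho 0.7:

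- unpaired: exp(2.228 × 0.472 × √(2/6)) = 1.84
- paired: exp(2.571 × 0.472 × √(0.6/6)) = 1.47

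| n | CV | Unpaired | Paired, rho 0.5 | rho 0.7 | rho 0.9 |
|---|---|---|---|---|---|
| 3 | 50% | 2.92 | 3.23 | 2.48 | 1.69 |
| 6 | 50% | 1.84 | 1.64 | 1.47 | 1.25 |
| 3 | 100% | 6.60 | 7.91 | 4.96 | 2.52 |
| 6 | 100% | 2.92 | 2.40 | 1.97 | 1.48 |

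**Break-even.** The paired interval is narrower only if rho > 1 − [t(2n − 2)/t(n − 1)]².

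- n = 6: 1 − (2.228/2.571)² = 0.25
- n = 3: 1 − (2.776/4.303)² = 0.58

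**Can raw values still show an effect?** The table gives power for a two-sided 5% t-test, used only as a yardstick because the plan has no test for these markers.

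| Assumed fall | CV | n | Raw values only | Paired, rho 0.5 / 0.7 / 0.9 |
|---|---|---|---|---|
| 50% | 50% | 3 | 0.28 | 0.31 / 0.44 / 0.80 |
| 50% | 50% | 6 | 0.63 | 0.82 / 0.95 / >0.99 |
| 80% | 50% | 3 | 0.87 | – |
| 80% | 50% | 6 | >0.99 | – |
| 80% | 100% | 3 | 0.44 | – |
| 80% | 100% | 6 | 0.85 | – |

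A large fall can therefore show in raw values, while a moderate one may not.

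**The case against.** The strongest reply is that Section 11 calls itself an outline and defers detail to a Statistical Analysis Plan. A promise to summarise does not exclude listings or profiles, and Section 11.4 allows documented changes. That is fair, but nothing in the text available for review commits to a change analysis. The same outline does specify change from baseline for the safety measurements.

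Several stronger readings are tempting, and the documents do not support them:

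- **The effect is lost.** This depends on CV, correlation and effect size, none of which is given. The 80% fall above shows that it need not be.
- **Pairing always helps.** At rho 0.5 the variance ratio suggests 1/(1 − 0.5) = 2 times as many patients. This ignores the lost degrees of freedom: at n = 3 the paired interval is wider. No interval is planned for these markers in any case.
- **Every patient has a baseline.** The sample is scheduled in each patient but is subject to separate consent.
- **Change from Day 8 isolates quizartinib.** Day 8 pre-dose already follows seven days of cytarabine and three of anthracycline (Section 5.3.1). No passage says that these markers fall with loss of circulating cells. If they do, a Day 15 or Day 21 ratio would fall too.
- **The earlier Phase 1 study is a template.** It used a whole-blood-based pSTAT5 assay, whereas Section 6.8.2 stores plasma, and this regimen is based on QuANTUM-First. It is a precedent only for reporting within patients, and it split results by FLT3-ITD status.

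One objection changes the remedy. In Cycle 1, the Day 8 pre-dose plasma precedes any quizartinib, so drug-related inhibition should be near nil and a ratio to it could be unstable.

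**Conclusion.** The point holds as a minor weakness of the analysis plan. The plan schedules a pre-dose sample but commits only to raw values per visit. That leaves out the spread of within-patient change and the number of patients with a decrease, and it exposes the visit means to missing samples. These gaps do not depend on any assumption about correlation.

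The gain in precision does. With 6 patients at CV 50%, the interval factor falls from 1.84 to between 1.64 and 1.25 for rho 0.5 to 0.9. With 3 patients it goes from 2.92 to between 3.23 (worse) and 1.69. An effect can be obscured; the documents do not show that it would be lost. The objective is secondary and exploratory, and the DLT and MTD decisions are untouched.

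**What to change.** In Section 11.3.5 and the synopsis, keep the raw summaries and add:

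1. For each phosphoprotein, each patient's ratio or percent change from the Day 8 pre-dose value, by time point and dose level, with FLT3-ITD status shown.
2. Individual profiles and the number of patients with a decrease. Both are informative at n = 3 whatever the correlation.
3. Plasma inhibitory activity displayed beside the same patient's pre-dose result, not as a ratio to it.
4. The Day 8 post-dose and Day 9 changes named as the main descriptive readout.
5. A statement that the pre-dose value follows chemotherapy, and that Day 15 and Day 21 changes cannot be attributed to quizartinib alone in a single-arm trial.

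The cost is a few sentences and some table columns, with no new sample, visit or patient. Fixing the baseline and time points beforehand also avoids choosing them after seeing data from 6 to 12 patients. The downside is that a patient without a Day 8 pre-dose value does not contribute to the change summary; the retained raw summaries still include that patient.
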